Uptake of PrEP in underserved areas outside of academic centers has been slow, leaving many high-risk individuals without access to this efficacious HIV prevention strategy.^(7, 24) HIV infection in the Southern United States is not limited to dense urban areas near academic medical centers, non-metropolitan Mississippi is at special risk because of the lack of local services, poverty and stigma.^(22, 25) Studies have found that MSM living in the rural South are more likely to have sex on their first date than urban men, possibly due to long travel distances and concern that the next sexual encounter may be a long time away. Additionally, rural venues where MSM openly socialize are scarce, resulting in men seeking sex partners via the Internet and by regularly traveling to higher seroprevalence areas. Our physicians at the University of Mississippi Medical Center (UMMC) are prescribing PrEP in their HIV/STI clinics in Jackson, MS but this only reaches 18% of the State's population. **PrEP is unavailable elsewhere in Mississippi, so 72% of the State is essentially underserved.**

Reaching this greatly at-risk population and evaluating effective methods for prevention of HIV infection is critical. PrEP clinical care follows a cascade that is similar to the HIV treatment cascade. The **PrEP cascade** includes screening a high-risk population, identifying candidates for PrEP, linkage to PrEP care, initiation of PrEP, retention in PrEP care, and adherence and persistence in PrEP clinical care.^(7, 24, 26, 27) Gaps arise at each step of the PrEP cascade and this proposed project will focus on addressing **identification, linkage, initiation, and adherence over 6 months** through a creative telemedicine/CBO link. Numerous studies indicate that many at-risk individuals will agree to, and successfully, take PrEP if it is easily available.^(9, 28) Unfortunately, many underserved populations have not yet been reached. By working with local CBOs, this project will reduce the barrier of distance and reach the underserved.

Local organizations are disinclined to prescribe or counsel patients about PrEP because they lack the needed resources and training. Previous research, clinical reports and the CDC have identified steps to introduce PrEP, provide counseling in risk reduction, and engage patients in continuing care.^(29,30)

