Tele-PrEP-MS Trial (Aim 2 - Year 2): Implement Tele-PrEP-MS in MS CBOs.

Recruitment and enrollment (see Human Subjects): All PrEP-eligible adult clients who present for HIV testing in the participating CBOs (not near UMMC) during the months of Aim 2 will be eligible to be enrolled in the online feasibility, acceptability and implementation survey. As noted in Aim 1, CBO staff will be trained in procedures to assist clients in obtaining necessary financial, transportation, and logistic resources for PrEP. They will collaborate with UMMC staff to resolve these issues for participants as they did in our recent Tele-PrEP-MS experience at a CBO.

PrEP Care Cascade estimates: Based on data from the CBO testing sites, UMMC HIV screening clinics, and our recent Tele-PrEP-MS experience in a CBO (see Preliminary Studies), it is estimated that a total of 600 adults (both sites combined, 25 per month at each month for 12 months) will present for HIV testing during Year 2. It is estimated that 300 (50%, which is less than the UMMC rate) will be PrEP-eligible (not HIV infected and with elevated risk scores). Because of COVID, the CBOs have discontinued the in-person events that led to most of their HIV testing. With permission of our NIMH program officer, [name], our survey recruitment goal was reduced from 240 PrEP-eligible to 25-50 and Aim 3 (qualitative assessment) was enhanced. We will enroll 25-50 (80%) of the PrEP-eligible in the assessments ⁽⁸⁴⁾. The sample will be 75% male (mainly MSM), 85% will be nonwhite, with mean age of 26 years. Of the 25-50 enrolled participants, 75%, which is less than our recent experience, will attend Tele-PrEP-MS with UMMC specialist, and 66.6%, which is less than our recent experience and more than the UMMC rate, will return within three months and will be taking PrEP. Adherence at 6 months will also be assessed.

Determinations of Tele-PrEP-MS acceptability and its associated factors (Aims 2 & 3, Year 3):

Aim 3: Determine the acceptability and feasibility of Tele-PrEP-MS and to examine the individual, organizational and structural factors associated with its acceptability and feasibility.

Analyses will occur with a mixed methods approach that includes interviews of stakeholders (clients, staff, and administrators), an online survey of clients obtained during the implementation phase in Aim 2, and aggregate clinic records.

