Primary outcomes

PrEP-related outcomes: The project will assess at 3 and 6 months: attendance at Tele-PrEP-MS session, receipt of PrEP, and adherence to PrEP by participant self-report and, with participants' knowledge and signed HIPAA authorization via DocuSign, abstraction from the electronic medical record. Because of travel and structural barriers, virtually no one will begin PrEP at another location, although the project will also assess this occurrence by participant self-report.

Protocol acceptability and patient – provider relationships: The Acceptability of Tele-PrEP-MS by clients, CBO staff, administrators and UMMC physicians will be assessed with modified versions of the

Session Evaluation Form (SEF) and the Client Satisfaction Questionnaire (CSQ-8), which have good reliability and validity.^(87, 88) These 21 items assess study procedures, quality and quantity of service, outcome, and general satisfaction using Likert-style items. In addition, patients and providers will complete two assessments focused on their perceived working relationships. The 12-item Working Alliance Inventory (WAI) measures perceptions of collaborative goals, tasks.⁽⁸⁹⁾ Another 5-item Likert scale, PrEP Collaboration, using items modified from the ART Adherence intervention, assesses mutual trust and understanding.⁽⁹⁰⁾ These quantitative data will supplement the analyses of the interviews of representative stakeholders to examine protocol acceptability and association of patient – provider relationships with demographic factors and PrEP outcomes.

Secondary outcomes (pre/post and follow-up assessments)

PrEP knowledge: Because there is no PrEP knowledge scale with published psychometrics, we will use a 15-item questionnaire to assess knowledge (true/false/don't know) based on facts from the CDC and the San Francisco AIDS Foundation websites concerning PrEP. The items will be tested for readability and relevance with the target population in the qualitative phase of the study. Items will be revised, if needed, for the RCT.

Motivational readiness for PrEP and PrEP-related care: Rollnick's Readiness Ruler(91) will be used to assess motivation for engaging in PrEP care using two items from 1 (not ready) to 10 (ready to engage).

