Aim 2: Determine the acceptability of Tele-PrEP-MS and to examine the factors associated with its acceptability. The Client Satisfaction Questionnaire (CSQ), the Session Evaluation Form (SEF) and the Working Alliance Inventory (WAI) will quantitatively assess acceptability according to patients attending Tele-PrEP-MS. In addition to scale scores, individual item mean scores and standard deviations will be reviewed to determine if there are specific elements of the protocol that are lacking in feasibility, appeal, relevance, or utility. Other scale scores (e.g. Motivation for PrEP) will be computed and non-scale items topically grouped (e.g. health literacy, housing).

Aim 3a: Examine PrEP-related outcomes over six months (proportions screened for PrEP eligibility; attending a PrEP medical evaluation; taking PrEP at 3 and 6 months) **to compare the academic medical center and the CBOs** (Exploratory). The UMMC HIV/STI screening clinics test 9,000 patients each year and approximately 65% are at high-risk for HIV (according to on-going analyses of the Risk Stratification data). Only one third return to initiate PrEP because wait times and distance are often barriers. These rates will be updated at UMMC for the trial year of this study and will be used to gauge the efficiency PrEP outcomes observed in Tele-PrEP-MS at the CBOs. As this is an exploratory aim, direction of effects is not predicted and the comparison is largely descriptive and to provide context for the results. Comparisons of proportions will be made using Chi Square analyses.

Aim 3b: Examine any factors related to these outcomes (Exploratory aim). Only the CBOs will have patient-level data to examine factors related to patients' PrEP outcomes. Relevant scale scores (e.g. Motivation for PrEP) will be computed and non-scale items topically grouped (e.g. health literacy, housing). Outcomes include Tele-PrEP-MS visit attendance (yes/no; clinic and self-report data), PrEP prescription accepted (yes/no; clinic and self-report), and adherence to PrEP (yes/no; clinic and self-report). For the enrolled PrEP-eligible group multiple logistic regression will be used to examine the predictive association of demographics (e.g. race, sexual orientation), baseline scales (e.g. motivation, skills), scale change scores (e.g. PrEP knowledge), and screening visit acceptability (CSQ, SEF, WAI scores) on each outcome.

Inclusion of Women, Minorities, and Children

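### Aim 3b analyses adherence, a listed primary outcome, only as an undefined yes/no; a graded self-report item would keep information that a sample of 25-50 can ill afford to lose

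*Combined protocol and SAP*

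**What the plan says.** All references are to the combined protocol and SAP.

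- **Primary outcomes, PrEP-related outcomes.** At 3 and 6 months the project assesses "attendance at Tele-PrEP-MS session, receipt of PrEP, and adherence to PrEP by participant self-report", supplemented by abstraction from the medical record. No adherence instrument, scale or threshold is named.
- **Quantitative Data Analytic Plan, Aim 3b.** The aim is to "Examine any factors related to these outcomes (Exploratory aim", so it is labelled exploratory. Attendance, acceptance of a prescription and adherence are each coded yes/no. The last is "adherence to PrEP (yes/no; clinic and self-report". Neither a cut-off nor a time point is given.
- **Model and analysis set, same section.** "For the enrolled PrEP-eligible group multiple logistic regression will be used to examine the predictive association of demographics", along with baseline scales, change scores and acceptability scores, on each outcome separately.
- **PrEP Care Cascade estimates.** Because of COVID, "our survey recruitment goal was reduced from 240 PrEP-eligible to 25-50". The plan expects 75% of those enrolled to attend a telemedicine visit, and 66.6% to return within three months and be taking PrEP.
- **Sources of Material.** The record-based measures are the telemedicine visit, receipt of PrEP and taking PrEP. None is graded.

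**The concern.** How much of a medication someone takes is naturally a matter of degree. A yes/no version puts a person who misses a few doses either with someone who has nearly stopped or with someone who misses none, depending on a cut that the plan does not state. Aim 3b is the only planned quantitative model relating patient and provider factors to PrEP outcomes. The section on recent experience with Tele-PrEP-MS names more precise cascade rates and their associated factors as a goal of the study. With the sample cut to 25-50, a coarse outcome makes it easier to miss a real association with motivation, self-efficacy or working alliance. A graded self-report not asked for at 3 and 6 months may not be recoverable later.

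**Working it through.** **1. What the plan's figures give.** The documents state no power, alpha or effect size for Aim 3b, so there is no power figure to reproduce. The recruitment chain behind the superseded goal does reproduce: 25 per month × 2 sites × 12 months = 600; × 50% = 300 eligible; × 80% = 240.

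**2. Expected number taking PrEP.** The base for 66.6% is unclear, so both readings are shown.
- Of attenders: 25 × 0.75 × 0.666 = 12.5, and 50 × 0.75 × 0.666 = 25.0.
- Of all enrolled: 25 × 0.666 = 16.7, and 50 × 0.666 = 33.3.

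This gives about 12-33 takers, before any survey non-response.

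**3. Loss from a cut, by formula.** Assumptions, none from the documents: two-sided 5% test, one predictor, a roughly normal graded score with correlation *r* to the predictor, and a share *p* coded *yes*. Cutting shrinks the correlation by a = φ(z_p)/√(p(1−p)). Power is about Φ(atanh(r)·√(n−3) − 1.96).

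Example with n = 25, r = 0.5, p = 0.667, so a = 0.771:
- Graded: 0.549 × 4.690 − 1.96 = 0.616, power 73.1%.
- Yes/no: r becomes 0.386; 0.407 × 4.690 − 1.96 = −0.05, power 47.9%.
- Loss: 25.2 points.

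**4. Simulation among takers.** Rank test on the graded score against a test on the yes/no cut:

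| n | r | Share *yes* | Share at maximum | Graded | Yes/no | Loss (points) |
|---|---|---|---|---|---|---|
| 17 | 0.4 | 70% | none | 35% | 22% | 13 |
| 25 | 0.4 | 70% | none | 50% | 31% | 19 |
| 33 | 0.4 | 70% | none | 62% | 42% | 20 |
| 17 | 0.5 | 70% | none | 53% | 33% | 20 |
| 25 | 0.5 | 70% | none | 72% | 49% | 23 |
| 33 | 0.5 | 70% | none | 84% | 61% | 23 |
| 25 | 0.5 | 80% | 50% | 63% | 40% | 23 |
| 25 | 0.5 | 70% | 70% | 51% | 47% | 4 |
| 17 | 0.5 | 70% | 70% | 36% | 33% | 3 |

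In the last two rows *yes* means being at the maximum. Only 25 × 0.3 = 7.5 people then fall below it, and the graded scale adds information only among them. Across runs of this kind the loss was about 1-4 points. At n = 12 and r = 0.3, with no such ceiling, it was about 3-5 points. In the other direction, an 80% split with no ceiling at all gives about 33 points by the formula (n = 25, r = 0.5: 73.1% against 40.3%), so 20-25 is not a strict upper limit.

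**5. The analysis set the plan names.** Aim 3b models everyone enrolled. People never on PrEP would then share one adherence value. With n = 25 or 50 and r = 0.3-0.5, the loss is about 3-12 points. Other assumption sets gave 0-9 points (half the patients tied) and 1-13 points (a wider mix of ceilings and cuts).

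**6. The cascade as one ordered outcome.** With shares of 25/25/50 (not attending, attending without PrEP, on PrEP), n = 50 and an odds ratio of 2 per SD, a single ordinal analysis has 68% power, against 62% for taking PrEP and 50% for attendance. In a four-level version (n = 25 or 50, r = 0.3-0.5) the gain over the adherence cut was 3-8 points.

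**The case against.** The best case for leaving the plan alone has four parts.

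- **Nothing graded may exist to be cut.** Adherence yes/no can be read as on or off PrEP, which is binary and available from both clinic record and self-report. This stands: a reader might infer that the plan collects a graded measure and throws it away, but no document describes one. The point is therefore to add an item, not to undo a cut.
- **Aim 3b is exploratory.** The Interview Analysis section describes Aim 3 as giving descriptive associations, and the qualitative part was enlarged when the survey shrank. This stands too, and means that no powered test is at risk. Precision still matters in an exploratory analysis.
- **Adherence may hardly vary.** In the pilot all 14 patients who returned were taking PrEP. If most takers report the maximum, little is lost. But those 14 were counted as taking PrEP, not by how much they took, so the pilot does not settle this.
- **The number of predictors is the larger limit.** All the figures above use one predictor; the plan lists many. Even graded power is only 35-72% for n = 17-25 and r = 0.4-0.5.

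A reader might also infer that an ordinal model of the furthest cascade step should lead. The documents do not support that. The Significance section says that gaps arise at each step, which suits step-specific models. A proportional-odds model assumes one common effect across steps, which 25-50 people can barely check. The gain over taking PrEP is about 6 points.

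**Conclusion.** The point holds as a cheap improvement to an exploratory analysis. Adherence is a listed primary outcome, is analysed only as yes/no, and is nowhere defined. If adherence varies among takers, a yes/no outcome loses information about the factors related to it.

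The size cannot be fixed from the documents. A reader might infer a flat loss of 10-25 points; that needs a near-continuous score, a moderate to strong correlation and a convenient split, none of which the plan states. The supportable range runs from about 1-4 points (a heavy ceiling that coincides with *yes*) to about 20-25 points (n = 25-33, r = 0.5, 70-80% *yes*, with a ceiling of half the takers in the 80% case). It is about 3-12 points in the full enrolled set with non-takers tied. The change does not make Aim 3b well powered.

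**What to change.** 1. Add one item to the 3- and 6-month REDCap surveys already planned: the number of days PrEP was taken in the past 30.
2. In Aim 3b, analyse that item on its full scale among those prescribed PrEP, by rank correlation or an ordinal model.
3. Keep the yes/no outcome from clinic record and self-report as a descriptive summary and cross-check. State what counts as *yes* and at which time point.
4. Keep the step-specific models. An ordinal analysis of the furthest cascade step is at most an optional supplement.

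**Cost.** One survey item and a few lines of analysis text, with no extra patients, visits or staff. The graded item rests on self-report alone, so the clinic record no longer feeds that analysis directly, which is why the yes/no outcome stays alongside. Answers may bunch at the maximum; a rank or ordinal method copes with ties but cannot restore spread that is not there. Restricting to those prescribed PrEP also departs from the enrolled group that Aim 3b now names, and the text should say so.

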Women. Participants in this study will be comprised of both females and males. It is anticipated that 25% of the sample will be females, reflecting the population of the HIV testing clinics from which the sample will be recruited, so women will be adequately represented.

Minorities. The aim of our recruitment strategy is for the resulting program materials to be appropriate for racial minorities in the South. We anticipate that in terms of race 73% of the enrolled participants will be Black/African American, 22% will identify as White, and 5% will identify as More than one race. Ethnically, 2% will self-identify as Hispanic or Latino.

Children. No children will be included in this project. PrEP was recently FDA-approved for youth under that age of 18 but the CDC has not yet released guidelines for its use. The aim of this study is to examine the use of telemedicine for PrEP among adults who are eligible for its use according to the FDA and using CDC guidelines.

Protection of Human Subjects and Safety Monitoring Plan

Human Subjects Involvement, Characteristics and Design

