Participants will be recruited from participating CBOs (not near UMMC). There will not be overlap between subjects in the formative phase and the implementation phase. Retention techniques for the study include maintaining updated participant contact information, frequent reminder cards, phone calls and emails, keeping records of friendship contacts, and obtaining the name and telephone number of another relative or family friend who would know of the patient's whereabouts. The retention rate in [name] previous community study (U01 MH066785) was 85% after 18 months.

Rationale for Including Special Classes of Subjects. N/A Special classes are not included in this project.
Sources of Material

Research Material Obtained from Living Human Subjects

Research material obtained from participants includes: 1) questionnaire data; 2) audio-tapes from interviews with patient participants, CBO staff, and UMMC physicians; and 3) Point-of-Care HIV test results.

For the formative phase, participants (patients, CBO staff, and UMMC physicians) will partake in interviews and will be asked questions regarding their perception of barriers or facilitators to implementation of telemedicine. These interviews will take place in private offices at the CBOs or UMMC. The audio-taped interview and written notes of the interview will be the sources of material for this phase. Additional interviews will occur after the trial phase. Interviews will be digitally recorded and kept in a secure location on the Rhode Island Hospital server. Interviews will inform the development of the protocol and provider training.

For the implementation phase of the study, patient participants will complete brief online questionnaires about their demographic, structural, and personal factors that may be associated with Tele-PrEP-MS. At baseline and follow-up, participants will complete an online survey about their knowledge around PrEP, protocol acceptability, motivational readiness for PrEP, PrEP & appointment self-efficacy, and perceived risk for HIV.

Questionnaires will be completed online via REDCap at entry to the study, and at 3-months and 6- months post-enrollment. PrEP-related measures (telemedicine PrEP visit, receipt of PrEP, and taking PrEP) will be obtained at the follow-up assessment time points from the electronic medical record.

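### Exploratory Aim 3b keeps ordinary multiple logistic regression after the survey was cut from 240 to 25-50; near 25 participants the model often has no finite fit, and no penalised method or fallback is named

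*Combined protocol and SAP*

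**What the plan says.** Under Quantitative Data Analytic Plan, Aim 3b covers attendance at the telemedicine visit, acceptance of a prescription and adherence, each coded yes/no. The method is given as: "For the enrolled PrEP-eligible group multiple logistic regression will be used to examine the predictive association of demographics". The predictor list continues: "baseline scales (e.g. motivation, skills), scale change scores (e.g. PrEP knowledge), and screening visit acceptability (CSQ, SEF, WAI scores) on each outcome". Race and sexual orientation are the demographic examples. That makes eight named terms: race, orientation, motivation, skills, knowledge change, CSQ, SEF and WAI. Five of them are examples only. The plan does not say whether all enter one model. It states no penalised or exact method, no final list, no coding of race and no rule for a model that will not fit.

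Under PrEP Care Cascade estimates, "our survey recruitment goal was reduced from 240 PrEP-eligible to 25-50". Of those enrolled, "75%, which is less than our recent experience, will attend Tele-PrEP-MS with UMMC specialist". For later PrEP use, the same section gives this forecast: "66.6%, which is less than our recent experience and more than the UMMC rate, will return within three months and will be taking PrEP". Two sections forecast race. The cascade section expects 85% nonwhite. Inclusion of Women, Minorities, and Children expects that "73% of the enrolled participants will be Black/African American, 22% will identify as White, and 5% will identify as More than one race".

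On the acceptability scales, the Aim 2 analysis text says that CSQ, SEF and WAI "will quantitatively assess acceptability according to patients attending Tele-PrEP-MS". Aim 3b ties the same scales to the screening visit. The section on research material obtained from participants says: "At baseline and follow-up, participants will complete an online survey about their knowledge around PrEP, protocol acceptability, motivational readiness for PrEP".

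**The concern.** A regression conceived for 240 people is now to be run on a tenth to a fifth of that number. When few people lack the outcome, some combination of predictors can divide the outcomes perfectly (complete or quasi-complete separation). Maximum likelihood (ML) then gives at least one odds ratio of zero or infinity. A yes/no predictor with a small group is especially exposed, because one empty cell is enough. ML models that do converge in samples this small tend to exaggerate odds ratios.

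Aim 3b is the plan's only regression of individual PrEP outcomes. Without a stated method for this case, the analyst would choose a remedy after seeing which model failed.

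A secondary question concerns the attendance model. A score that non-attenders lack, or a change score measured after the visit, cannot predict attendance.

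**Working it through.** **The plan's own figure.** 2 sites x 25 per month x 12 months = 600 tested; x 0.50 = 300 eligible; x 0.80 = 240. The former goal reproduces.

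**Size of the smaller outcome group.**
- Non-attenders: 0.25 x 25 = 6.25 and 0.25 x 50 = 12.5, against 0.25 x 240 = 60 before.
- Per term with eight terms: 6.25/8 = 0.78; 12.5/8 = 1.56; 60/8 = 7.5.
- Taking PrEP: the base of the 66.6% is unclear. It is either 66.6% of those enrolled or 0.75 x 0.666 = 50%.
- Outcome rates of 75%, 66.7% and 50% were therefore used. Prescription acceptance and adherence have no planning rate, so the last two serve as proxies.

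**Race alone, exact, with outcome unrelated to race.** With k people in one group and n-k in the other, and outcome rate p, the chance of at least one empty cell is

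1 - (1 - p^k - (1-p)^k)(1 - p^(n-k) - (1-p)^(n-k)),

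averaged over k ~ Binomial(n, share). As a rough check at n=25 with a 73/27 split, the smaller group has about 0.27 x 25 = 6.75, say 7, people. All 7 attend with probability 0.75^7 = 0.13. Averaging over the random group size gives 18.3%.

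| Race split | n=25, rates 75 / 66.7 / 50% | n=50, rate 75% |
|---|---|---|
| 73/27 | 18% / 10% / 5% | 3% |
| 85/15 | 40% / 32% / 25% | 15% |

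The 85/15 row does not count samples with nobody in the smaller group as failures (0.85^25 = 1.7% at n=25).

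With the three categories 73/22/5, failure at the 75% rate is 67% at n=25 and 56% at n=50. The 5% level then holds only 0.05 x 25 = 1.25 to 0.05 x 50 = 2.5 people. Merging levels would remove that part.

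**Several predictors, simulated.** Assumptions:
- true odds ratio 2.0 per SD for motivation, all other terms null;
- race binary at 0.73 (from the plan) and orientation binary at 0.65 (assumed);
- scales standard normal, with CSQ, SEF and WAI correlated at 0.5 (assumed).

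Separation was checked by linear programming. No finite fit means at least one infinite estimate; other coefficients can still be finite. Rates in order 75 / 66.7 / 50%:
- Eight terms, n=25: 49% / 32% / 20%. Repeat runs with other seeds gave about 48-53% at the 75% rate and 16-34% at the other two.
- Eight terms, n=37: 15% / 6% / 2%.
- Eight terms, n=50: 4% / 1% / 0.2%.
- Four terms (motivation, race, orientation, skills), n=25: 28% / 16% / 7%.
- One to three continuous scales only, n=25: at most 3%.
- Eight terms, n=240, 75% rate: no failures, median ML odds ratio 2.05.

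**Sensitivity.** Changed assumptions were race at 22% White, orientation at 30%, all scales correlated at 0.3, and log odds ratio per SD of 0 to 0.4 for every term. The eight-term attendance model then fails in 50-80% at n=25 and 7-25% at n=50.

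**Estimates for a true odds ratio of 2.0, eight terms.** The median among ML fits is 2.6-3.1 at n=25 and 2.4-2.5 at n=50. Firth's method gives medians of about 1.7-2.0. It was finite in 1,999 of 2,000 datasets in the worst cell; the exception had a constant or collinear predictor. Its typical 95% interval at the 75% rate is 0.6-13.7 at n=25 and 0.9-4.7 at n=50. With four terms it is 0.7-7.4 and 1.0-4.4.

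**Timing, by comparison of the text.** Surveys are listed at enrolment, 3 months and 6 months. The telemedicine visit is planned within a week of testing. The heading for secondary outcomes mentions pre/post assessments without saying whether a post score exists before 3 months. If it does not, a knowledge change score would postdate the visit.

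**The case against.** The strongest reply is that this is a small gap in a pilot. Aim 3b is exploratory and carries no alpha or power claim. The sample cut was paired with an enlarged interview component that examines the same factors. All of that stands, and it limits the weight of the point. It does not alter the regression text, which still commits to an ordinary model.

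A second reply is that failure is concentrated near n=25 with many terms, and that the plan never says all eight enter together. This also stands. The recruitment section hopes for at least 25-50, and the base-case failure rate falls quickly as n rises. A reader might infer that the regression is unworkable throughout the 25-50 range. The figures do not support that.

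A reader might also infer that dropping predictors is no cure. That holds only for models that keep sparse yes/no terms. Six of the eight named terms are scales, and one to three of those almost always fit. Yet race is the first predictor named, and it can fail alone.

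Third, exact logistic regression or purely descriptive tables would also fill the gap, and Firth adds no information. True: the intervals stay wide. Firth is suggested because it keeps mutual adjustment and almost always yields finite estimates.

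Finally, a reader might infer that non-attenders have no CSQ, SEF or WAI scores. The documents do not establish this. The screening-visit wording in Aim 3b and the baseline survey description suggest that everyone enrolled may have them; the Aim 2 wording points the other way.

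**Conclusion.** The point holds as a planning gap in an exploratory analysis and should be fixed before the data are analysed. At n=25 with 75% attendance, roughly half of eight-term models lack a finite estimate for at least one odds ratio, and about 17-34% do at rates of 50-67%. With four terms including race and orientation the figure is about 7-28% at n=25. At n=50 the eight-term figure is about 4% or less in the base case.

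That reassurance at n=50 depends on how race is split. Race alone fails in 3% with the 73/27 split but 15% with the 85/15 split, both at a 75% rate, and the plan's two race forecasts disagree. Exaggeration of odds ratios persists at n=50.

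These figures rest on the assumed joint entry of terms, the assumed prevalence of orientation, the effect size and the scale correlations. It would be wrong to conclude that the study's main findings are at risk, since no primary conclusion rests on Aim 3b. The timing of the acceptability scales is a request for clarification, not a demonstrated error.

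**What to change.** In Aim 3b, state that:
- models will use Firth-penalised logistic regression;
- a short predictor list, and the coding of race and sexual orientation, will be fixed before analysis;
- odds ratios with 95% penalised-likelihood intervals will be reported descriptively, without significance claims.

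A hard cap of one or two predictors is not needed.

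As a secondary clarification, reconcile the Aim 2 and Aim 3b analysis text, the research-material section and the secondary-outcomes heading on who completes CSQ, SEF and WAI, when they do so, and what pre/post means. Keep out of the attendance model any scale that non-attenders do not have and any change score measured after the visit.

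The cost is analysis-plan wording only, with no added participants or data. The downsides are slight shrinkage (a median of about 1.7-2.0 for a true 2.0), intervals that stay wide, and the need for a program that offers the method. The data-handling text names SPSS only as an example, so the choice is open.
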